1.2 Secondary Objectives

Assess the acute toxicity and quality of life scores in subjects after SBRT and RP.
Assess negative margin rate and neurovascular bundle preservation rate.

1.3 Exploratory Objectives

Analyze tumor and normal biopsied and resected tissue and serum markers.
Interpret interfraction and intrafraction MRI of prostate and seminal vesicles.

2 Background

2.1 Disease

Prostate cancer is the most common non-cutaneous cancer in men and the second leading cause of cancer death in men ¹. It is predicted that the number of cases will almost double by 2030 (GLOBOCAN 2012). The standard of care for patients with high-risk prostate include radiotherapy with androgen deprivation therapy (ADT) or prostatectomy which may be followed by adjuvant therapy ². Radical prostatectomy is the most common treatment for prostate cancer according to the National Cancer Institute's Pattern of Care study from 14 regional cancer registries with the proportion of men undergoing prostatectomy was 70% for age <60 years, 51% for 60-64 years, and 39% for 65-75 years ³. An increasing number of patients with high-risk prostate cancer are undergoing primary radical prostatectomy with a 20% increase from 2004 to 2012 ⁴.

High-risk features for recurrence include extra-capsular extension and/or seminal vesicle invasion (pT3 disease) and positive surgical margins, which occur in an estimated 20% and 16% of patients, respectively ⁵. Post-prostatectomy radiotherapy to the prostate bed for pT3 disease or positive surgical margins has been shown to reduce the risk of recurrence in three

randomized trials: Southwest Oncology Group, European Organization for Research and Treatment of Cancer and Auckland Radiation Oncology⁶⁻⁸. As such, adjuvant radiotherapy after prostatectomy is the standard of care for patients with pT3 disease, positive margins or Gleason Grade 8-10².

2.2 *Rationale*

Patients at high risk of recurrence are recommended to undergo post-operative radiotherapy as a surrogate to eradicate subclinical disease. The clinical target volume (CTV) is the prostate bed which is difficult to delineate once the prostate has been surgically removed and can be overestimated by the utilizing location of surgical clips⁹. As such, controversy exists in the field as to the optimal target volume. National and international guidelines suggest including a significant portion of the posterior and inferior aspects of the bladder, and anterior aspect of the rectum, exposing a significant amount of normal tissue to high dose radiation¹⁰⁻¹². Additionally, post-operative radiotherapy is delivered in 37-39 fractions over the course of 7 weeks, representing a high burden of therapy, which may be related to lower utilization of post-operative radiotherapy¹³.

Modern radiotherapy for untreated prostate cancer has been afforded many advantages including improved target delineation with multiparametric MRI and image-guided radiotherapy allowing for larger dose delivery in fewer fractions and tighter margins with stereotactic body radiotherapy (SBRT)¹⁴. Moreover, newer technologies with MRI based image guided radiotherapy with the ViewRay® and MRIdian linear accelerator now available at NewYork-Presbyterian/Weill Cornell Medicine will allow for significantly improved daily adaptive target delineation.

In patients that are likely to need radiotherapy after RP, the potential advantages of SBRT delivered over 5 fractions *prior* to surgery (preoperative) are: 1) reduced radiation dose to normal tissues, 2) increased convenience to patients because of fewer treatment days, 3) reduced costs to patients because of reduced travel expenses and copays, 4) improved resource utilization for physicians because of the fewer number of treatments per patient and overall and consequently 5) reduced cost to society. In prostate cancer specifically, SBRT has the added potential of not increasing toxicity while delivering a higher biological dose and therefore increased efficacy¹⁶.

2.3 *Risk/Benefit Assessment*

Two prior phase I trials have explored preoperative radiotherapy prior to prostatectomy for patients with high risk prostate cancer. A trial at Duke University treated the patients' prostate and seminal vesicles in a dose escalation fashion in 1.8 Gy daily fractions to total doses of 39.6 Gy, 45 Gy, 50.4 Gy and 54 Gy. **Acute GU and GI toxicities were limited to Grade 1 and no observed intraoperative complications occurred.** Late urinary toxicity was within the range expected for adjuvant radiotherapy ¹⁷. A trial at Princess Margaret Hospital utilized a preoperative dose of 25 Gy delivered in 5 fractions without image guidance. Similar to the trial at Duke University, **there were no observed intraoperative complications and urinary toxicity was within the range expected for adjuvant radiotherapy** ¹⁸. The current trial has the potential benefit of limiting radiation dose received by normal tissues that would be exposed in the postoperative setting, namely the bladder and rectum, with advanced image guided and dose delivery techniques. Additionally, as the prior phase I preoperative study using a hypofractionated dose of 25 Gy in 5 fractions did not demonstrate significantly different toxicities or any observed intraoperative complications, this study will begin at that dose level of 5 Gy x 5.

3 Subject Selection

3.1 Study Population

Subjects with a diagnosis of high-risk prostate cancer who meet the inclusion and exclusion criteria will be eligible for participation in this study.

3.2 Inclusion Criteria

1. Men aged ≥ 18 with histologically confirmed primary prostate cancer.
2. KPS ≥ 70
3. Patient with a negative staging bone scan.
4. Patient can undergo an MRI.
5. Patient with negative staging CT or MRI of pelvis. Suspicious evidence of nodal involvement on staging CT or MRI of pelvis is defined as greater than 1 cm on short axis. Documented negative biopsy of suspicious node required.
6. Patient is medically fit to undergo prostatectomy.
7. Patient has either Gleason Score ≥ 8 on biopsy and/or clinical/radiographic evidence of T3 disease.

3.3 Exclusion Criteria

1. Prior history of receiving pelvic radiotherapy.
2. Patient is unwilling to undergo prostatectomy.
3. Patient with active inflammatory bowel disease defined as currently receiving therapy for IBD.

4 Registration Procedures

4.1 Patient Registration

Once patient signs consent, please notify via email to [contact]. ROCTO will begin registration process as soon as the signed consent and the eligibility documents are obtained either as hard or soft copies.

Patients will be centrally registered in onCORE by ROCTO. To register a patient, upload the following documents to onCORE:

- Signed Informed consent
- Email the completed eligibility document to CancerCTRegistrar.

Registration must be completed within 24 hours of the signing of informed consent.

5 Study Calendar

5.1 Table 1. Schedule of trial events

	Screening	Before Radiation	Day 1 – Day 5 Radiation therapy					Tumor assessment (pre-surgery)	Surgery (less than 4 weeks post RT)	Follow up 1month post-surgery and q3months for 5 years
Radiotherapy			X	X	X	X	X			
Surgery									X	
EPIC SCORE		X							X	X*
IPSS		X							X	X*
Informed consent	X									
Demographics/Medical history	X									
Physical exam	X						X		X	X
PSA serum	X								X	X*
CT or MRI pelvis (with and without contrast)	X							X		
Adverse Events	X						X		X	X
Immune monitoring samples		X					X			X*

* - These procedures are required per protocol at the 1st follow up visit (post-surgery) only.

5.2 Screening Visit

- Informed Consent
- MRI pelvis
- Medical History, demographics and any baseline adverse events
- Routine Physical exam
- Serum PSA

5.3 Imaging Studies

Patients enrolling on the protocol will be treated as follows. Patients will be instructed to undergo a Fleet enema prior to planning CT/MRI and prior to each SBRT treatment.

Treatment planning CT/MRI will be performed with vac loc immobilization. Patients will be advised to drink 1-2 cups of water 1 hour prior to the CT/MRI simulation to allow for a comfortably full bladder, if tolerated. A rectal catheter will be utilized to dispel any excess

5.4 Radiation Treatment Planning

Three (3) patients will initially receive 5 Gy for 5 fractions. If patients tolerate the dose and undergo surgery without a post-operative Grade 3 or higher DLT 30 days, another set of 3 patients are selected for the next dose level. If the patients are to develop a post-operative Grade 3 or higher DLT, the trial will accrue additional 6 patients to the previous dose level.

The treatment planning CT will be fused to the T2 sequence of the MRI. The prostate + seminal vesicles (SV) will be contoured as the clinical target volume (CTV). The PTV expansion for the CTV will be 3-5 mm depending on physician discretion.

The bladder, femoral heads, penile bulb will also be contoured as normal structures.

The CTV (prostate + SV) will be treated to the prescribed dose (5, 6, or 6.5) Gy in 5 fractions.

VPrescription Dose (5, 6, or 6.5) Gy (volume of the PTV receiving Prescription (5, 6, or 6.5) Gy should be $\geq 95\%$)

18

- Gy,
1. Rectum: Maximum dose to 1 cc 38.5 Gy, Max dose to 3 cc 34.4 Gy, D53% 24
Max point dose 40 Gy
 2. Bladder: Maximum dose to 1 cc 38.5 Gy, Max point dose 40 Gy
 3. Penile Bulb: No more than 105% of prescription dose; D3cc 25 Gy. This is a
soft constraint.
 4. Femoral heads: Maximum point dose 30 Gy
 5. Small bowel: Maximum point dose 25 Gy
 6. Urethra: Max dose 38.78 Gy

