escalation and de-escalation study to determine maximum tolerated dose (MTD) and the recommended phase II dose (RP2D) based on acute toxicity measures. Part 2 will be a cohort expansion study to further evaluate the safety and tolerability of the RP2D based on toxicities measured at 1 year.

In part 1 of the study, a modified dose escalation and de-escalation design with an expansion of 3 or 6 patients to allow the recommended phase II dose (RP2D) be examined in a total of 9 patients will be used. The dose limiting toxicity (DLT) is defined as Grade 3 or higher (G3+) gastrointestinal (GI) and/or urinary (GU) AEs related to preoperative radiotherapy according to the Clavien-Dindo Classification at 30 days. Three radiation dose levels, 5 Gy, 6 Gy and 6.5Gy are considered. A 3+3 dose escalation plan will be used. At the start of each dose level k ($k=1, 2$, or 3), 3 patients will be enrolled and treated for five days. If none of the 3 patients develop the DLT, the testing dose will escalate to the next level, $k+1$. If 1 of the 3 patients develops the DLT, the current dose will be tested in an additional 3 patients. If no additional patients develop the DLT, the dose will escalate. If 1 of the additional 3 patients develops DLT, i.e. a total of 2 of 6 patients with DLT, the previous dose will be deemed the maximum tolerated dose (MTD) and tested in a total of 9 patients. If ≤ 2 among the 9 patients experience the DLT, this dose will be considered as the RP2D. If ≥ 2 of 3 patients or ≥ 2 of 6 patients develop DLT, the study will stop without MTD if $k=1$ or consider dose level $k-1$ to be the MTD and tested in an additional 3 or 6 patients so that a total of 9 patients are evaluated. If ≥ 3 of 9 patients experience the DLT, the de-escalation will continue. This design ensures that the DLT rate to be $\leq 2/9$ for the RP2D.

In part 2 of the study, additional 21 patients will be enrolled to further examine the safety of the R2PD in a total of 30 patients. The primary safety endpoint will be G2+ GI and/or GU AEs related to preoperative radiotherapy according to the CTCAE v5.0 measured at 1 year. Patients will be continuously monitored to ensure the acute G3+ GU and/or GI AEs based on the Clavien-Dindo Classification at 30 days do not exceed 4 of 18 patients, and 6 of 27 patients.

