8.2 Sample Size/Accrual Rate

The sample size for part 1 portion of the study will vary depending on the number of patients that develop the DLT. If no DLTs are seen, we will recruit $3+3+3+6=15$ patients at 5, 6, and 6.5 Gy, respectively. Following the schema above, the maximum number recruited would be 27, which would only occur if 0 of 3 or 1 of 6 patients develop the DLT in dose escalation phase but >2 of 6 or >1 of 3 patients in the expansion cohort develop the DLT, triggering an expanded cohort at a lower dose.

Sample size for part 2 portion of the study will be 30 including the 9 patients from part 1. Having a total of 30 patients in the expansion cohort will allow us to estimate the 1-year G2+ toxicity rate based on CTCAE v5.0 within a 95% CI width of 0.37 and help with the decision making at the end of the trial. For example, an observation of ≥ 8 of the 30 patients having G2+ toxicity at 1-year based on CTCAE v5.0 would suggest that the probability of the toxicity rate being > 0.20 is greater than 80%, which will allow us to make an informative decision on whether the R2PD is worth to be examined at a larger trial.

8.3 *Stratification Factors*

No stratification factors are planned for the primary endpoint.

8.4 *Analysis of Endpoints*

8.5 *Analysis of Primary Endpoints*

Primary endpoints for this study are G3+ GU and/or GI toxicities at 30 days based on Clavien-Dindo Classification (Part 1) and G2+ GU and GI toxicities at 1 year based on CTCAE v5.0 (Part 2). Adverse events based on the two classification systems will be recorded. Descriptive statistics including the number, proportion of patients experience AEs, and 95% confidence interval of the proportion estimate calculated using the Clopper-Pearson method will be summarized. The analysis set will include patients who receive any dose of the preoperative radiation therapy.

8.6 *Analysis of Secondary Endpoints*

Assessment and analysis of secondary endpoints including toxicity and quality of life scores will be descriptive.

8.7 *Interim Analysis*

This study will have interim analyses after every dose in the sense that if any unacceptable dose limiting toxicities are seen, future patients will be recruited at a lower dose.

9 *Adverse Event Reporting Requirements*

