10.2 Stopping Rules

For Part1, after completion of a dose level, if ≥ 2 of 3, ≥ 2 of 6 or ≥ 3 of 9 patients develop a post-operative gastrointestinal or urinary grade 3 or higher toxicity at 30 days related to preoperative radiotherapy, the trial will accrue patients to the previous lower dose level. If ≥ 2 of 3, ≥ 2 of 6 or ≥ 3 of 9 patients develop a post-operative gastrointestinal or urinary grade 3 or higher toxicity at 30 days related to preoperative radiotherapy at 5 Gy x 5 fractions, the trial will stop. During Part 2, the study will stop if ≥ 5 of 18, or 7 of 27 patients develop a post-operative gastrointestinal or urinary grade 3 or higher toxicity at 30 days related to preoperative radiotherapy at the R2PD. Adverse events at 30 days will be recorded based on according to the Clavien-Dindo Classification.

If safety concerns arise, the DSMB will identify these concerns and recommend modification or termination of the clinical trial. There is no formal interim analysis for this trial.

11 References

2. NCCN Clinical Practice Guidelines in Oncology - Prostate Cancer (Version 2.2017). (2017).
3. Hamilton, A.S., *et al.* Trends in the treatment of localized prostate cancer using supplemented cancer registry data. *BJU Int* 107, 576-584 (2011).
4. Weiner, A.B., *et al.* Contemporary management of men with high-risk localized prostate cancer in the United States. *Prostate Cancer Prostatic Dis* 20, 442 (2017).
5. Tewari, A., *et al.* Positive surgical margin and perioperative complication rates of primary surgical treatments for prostate cancer: a systematic review and meta-analysis comparing retropubic, laparoscopic, and robotic prostatectomy. *Eur Urol* 62, 1-15 (2012).
6. Thompson, I.M., Jr., *et al.* Adjuvant radiotherapy for pathologically advanced prostate cancer: a randomized clinical trial. *JAMA* 296, 2329-2335 (2006).
7. Bolla, M., *et al.* Postoperative radiotherapy after radical prostatectomy for high-risk prostate cancer: long-term results of a randomised controlled trial (EORTC trial 22911). *Lancet* 380, 2018-2027 (2012).

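### Section 5.4, read literally, lowers the dose after any Grade 3+ DLT, whereas Section 8.1 adds 3 patients at the same dose after 1 DLT in 3

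*Combined protocol and SAP*

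**What the plan says.** Section 5.4 (Radiation Treatment Planning) has two branches after the first three patients. If they undergo surgery without a Grade 3 or higher DLT, "another set of 3 patients are selected for the next dose level". Otherwise the text reads "If the patients are to develop a post-operative Grade 3 or higher DLT", and the action is that "the trial will accrue additional 6 patients to the previous dose level". It does not say how many DLTs trigger this, and it does not refer to Section 8.1.

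Section 8.1 (Study Design/Endpoints) gives a full algorithm: "A 3+3 dose escalation plan will be used". Its middle branch is explicit: "If 1 of the 3 patients develops the DLT, the current dose will be tested in an additional 3 patients". Then: "If no additional patients develop the DLT, the dose will escalate". Two or more DLTs in 3 or in 6 make the level below the MTD, which is topped up with 3 or 6 patients to a total of 9. At the lowest level the study stops without an MTD. Three or more DLTs in 9 continue the de-escalation.

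Section 8.2 gives a Part 1 size of 15 with no DLTs and a maximum of 27, "which would only occur if 0 of 3 or 1 of 6 patients develop the DLT in dose escalation phase" and the expansion cohort then shows too many DLTs.

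Section 10.2 (Stopping Rules) says that at 2 or more of 3, 2 or more of 6, or 3 or more of 9, "the trial will accrue patients to the previous lower dose level". At 5 Gy x 5 the same counts stop the trial.

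**The concern.** These are two current passages on the same decision: which dose the next patients receive. They part after exactly 1 DLT in the first 3. Section 5.4, taken at its word, sends 6 patients to the level below; Section 8.1 sends 3 patients to the level just tested and may then escalate.

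Section 5.4 is also incomplete in two further ways. At 5 Gy there is no previous level to return to. And its fixed 6 agrees with Section 8.1 only when the lower level has treated 3 patients; if that level already holds 6, adding 6 gives 12 rather than the planned 9.

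Staff who work from the treatment section would lower the dose after a single event that the design is meant to tolerate. What is at stake is an RP2D set too low, not excess toxicity.

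**Working it through.** **The plan's own figures.** Under Section 8.1 with no DLTs, Part 1 recruits 3 + 3 + 3 + 6 = 15. The maximum is 3 levels x 9 patients = 27. Both match Section 8.2. These totals do not by themselves separate the two rules. The six-patient outcomes do: under a literal Section 5.4 a level holds 3 patients, or 9 after a top-up, but never 6. The 1 of 6 in Section 8.2 and the 2 of 6 in Section 10.2 could not then arise. So Sections 8.1, 8.2 and 10.2 belong together and Section 5.4 is the odd one out.

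**Inputs.** The cohort sizes and thresholds come from Sections 5.4, 8.1 and 10.2. The documents state no true DLT rate, so p = 5%, 10%, 20% and 30% are illustrative. Section 5.4 is read as lowering the dose after any DLT in 3. Write q = 1 - p.

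**Step 1: how often the rules diverge.** P(exactly 1 of 3) = 3pq². At p = 10% this is 3 x 0.10 x 0.81 = 24.3%.

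**Step 2: chance that a level fails the escalation step.**
- Section 5.4: 1 - q³. At 10%: 1 - 0.729 = 27.1%.
- Section 8.1: P(2 or more of 3) + 3pq² x (1 - q³). At 10%: 0.028 + 0.243 x 0.271 = 9.4%.

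**Step 3: top level expanded to 9.** Section 8.1 adds the failure probability q³ x P(Bin(6,p) ≥ 3) + 3pq² x q³ x P(Bin(3,p) ≥ 2). Section 5.4 has no check at 9 patients; if the 3-of-9 check is borrowed from Section 8.1, it adds q³ x P(Bin(6,p) ≥ 3). At 10%, P(Bin(6,p) ≥ 3) = 0.01585, so Section 8.1 becomes 0.0939 + 0.0165 = 11.0% and Section 5.4 becomes 0.271 + 0.0116 = 28.3%.

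**Step 4: chance that 6.5 Gy becomes the RP2D.** This assumes the same DLT rate at all three levels and the 3-of-9 check under both rules.
- Section 5.4: (q³)³ x P(Bin(6,p) ≤ 2). At 10%: 0.729³ x 0.98415 = 38.1%.
- Section 8.1: (q³ + 3pq² x q³)² x [q³ x P(Bin(6,p) ≤ 2) + 3pq² x q³ x P(Bin(3,p) ≤ 1)]. At 10%: 0.906² x 0.890 = 73.0%.

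**Results (exact binomial).**

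| True DLT rate | Exactly 1 of 3 | Fails escalation step, 5.4 vs 8.1 | Fails as top level with 9, 5.4 (borrowed check) vs 8.1 | 6.5 Gy is RP2D, 5.4 (borrowed check) vs 8.1 |
|---|---|---|---|---|
| 5% | 13.5% | 14.3% vs 2.7% | 14.5% vs 2.9% | 62.9% vs 92.0% |
| 10% | 24.3% | 27.1% vs 9.4% | 28.3% vs 11.0% | 38.1% vs 73.0% |
| 20% | 38.4% | 48.8% vs 29.1% | 53.9% vs 36.2% | 12.1% vs 32.0% |
| 30% | 44.1% | 65.7% vs 50.6% | 74.5% vs 62.6% | 3.0% vs 9.1% |

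**The case against.** The best defence is that Section 5.4 is a loose summary, not a competing rule. It speaks of the patients collectively and nowhere says that one event is enough. Its 6 is what Section 8.1 prescribes when stepping down to a level that has treated 3, and the number has no other evident source. The section is mainly about contouring and dose constraints, while Sections 8.1 and 10.2 state the algorithm in full, including the stop at 5 Gy. On that reading a 1-of-3 cohort is never sent down, and the contrasts above have no basis.

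This reading is possible, but it does not rescue the text. Section 5.4 would then give no instruction for 1 of 3, would still be silent on the lowest dose, and would still fix the top-up at 6 where Section 8.1 allows 3 or 6.

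The limits on the figures stand. The RP2D column describes a hybrid, because Section 5.4 defines no RP2D and no check at 9 patients. An equal DLT rate at three rising doses is a simplification. At rates of 20% to 30%, selecting 6.5 Gy less often is not clearly a loss. The step 1 and step 2 figures need no borrowed rule, although they too rest on assumed rates, and step 2 also rests on the any-DLT reading.

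**Conclusion.** The concern holds. Section 5.4 is wrong on its literal reading and incomplete on the charitable one. After exactly 1 DLT in 3, it does not give the instruction that Section 8.1 gives. For assumed DLT rates of 5% to 30%, this situation arises in 13.5% to 44.1% of three-patient cohorts. If Section 5.4 is followed literally, the chance of failing an escalation step rises by 11.6 percentage points at 5% (14.3 - 2.7), 17.7 at 10% (27.1 - 9.4), 19.7 at 20% (48.8 - 29.1) and 15.1 at 30% (65.7 - 50.6).

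The effect is towards a lower dose, no stated sample size or threshold changes, and a careful reader can find the intended rule elsewhere. It should be fixed because it is a dose-assignment instruction in the treatment section, but it does not undermine the design.

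**What to change.** In Section 5.4, replace the escalation and de-escalation sentences with a statement that dose assignment follows the algorithm in Section 8.1 and the thresholds in Section 10.2. Optionally, define the unacceptable toxicities mentioned in Section 8.7 by the same thresholds; Section 8.7 is not a separate conflicting rule. The cost is amendment wording only, and the 15 and 27 in Section 8.2 stay as they are. The documents do not state accrual status; if Part 1 is already complete, the report should say which rule governed each cohort.

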5.5 Trial Procedures

The Study Procedures [Section 5.1](#) summarizes the trial procedures to be performed at each visit. It may be necessary to perform these procedures at unscheduled time points if deemed clinically necessary by the investigator.

5.6 General Concomitant Medication and Supportive Care Guidelines

- a. Urinary: A proportion of patients undergoing prostate SBRT can expect increase in urinary frequency or urgency. If this becomes bothersome to the patient, medication to alleviate symptoms can be prescribed at the discretion of the treating radiation oncologist and documented in patient chart.
- b. Bowel: Bowel symptoms during time of prostate SBRT are rare. If patients develop rectal urgency, tenesmus or diarrhea, medication to alleviate symptoms can be prescribed at the discretion of the treating radiation oncologist and documented in patient chart.

